1.3 Secondary Objective

- To assess the safety and tolerability of combination therapy with pembrolizumab plus radium-223
- To preliminarily investigate the efficacy of the combination of pembrolizumab plus radium-223 as evaluated by progression-free survival (PFS) and overall survival (OS)

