13. STATISTICAL CONSIDERATIONS

13.1 Study Design/Endpoints

This is an open label phase 2 trial that randomizes 45 mCRPC patients (2:1 ratio) to radium-223 plus pembrolizumab combination therapy or to radium-223 monotherapy. The primary objective is to compare the increase in immune CD8+ and CD4+ T cell infiltration levels from baseline to 8 weeks on treatment between the two treatment arms.

Primary Endpoint:

Difference in tissue immune cell (e.g., CD4+/8+T) infiltration in the bone metastasis biopsy specimens from baseline to 8 weeks on treatments in both the combination and monotherapy arms.

Secondary Endpoints:

- Safety and Tolerability: grade 3 or higher adverse events that are considered treatment related according to NCI CTCAE (version 4.0)
- Progression-free survival (PFS): is defined as the time from the first dose of study drug to the earlier of the first documentation of definitive disease progression [as

defined by Response Evaluation Criteria in Solid Tumors (RECIST version 1.1) and PCWG2] or death due to any cause. Participants alive without disease progression are censored at date of last disease evaluation

• Overall survival as defined in 11.1.8

Exploratory Endpoints:

- Clinical-based endpoints
 - Changes in PSA
 - PSA response: defined as decline ≥50% from baseline to 12 weeks of therapy and which has been confirmed with a second PSA at ≥ 3 weeks later
 - Time to PSA progression as defined in 11.1.9
 - Time to normalization of alkaline phosphatase (if initially elevated)
 - Time to decrease in alkaline phosphatase (if initially elevated)
 - Symptomatic skeletal events (SSEs): Rate of SSEs and time to first SSE
 - Changes in osteoblastic activity on bone scan (assessed using the quantitative SPECT/CT)
 - Changes in quality of life, pain, and analgesic use, and time to introduction of analgesics
 - Immune-based endpoints
 - Quantify the CD8, CD4, and FoxP3+ CD4 (Treg) cell infiltration in the bone biopsy specimens, and to subsequently quantify the CD8/Treg and CD4/Treg ratios
 - Change in circulating T cell clonality
 - Induction of IgG antibody response
 - Changes in PD-L1 expression and co-regulation of other immune checkpoints such as TIM-3, LAG-3, and PD-L2
 - Changes in immunosuppressive cell populations and cytokines (e.g., MDSCs, Tregs, TGF-β, and iNOS)
 - Change in serum chemokines: (e.g., CXCL9, CXCL10)

- Changes in soluble PD-L1 ([name] Lab assay)
- Genomic-based endpoints

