13.3 Stratification Factors

Patients will be stratified based on:

- Baseline alkaline phosphatase <220 or ≥ 220
- Volume of bone metastases (high: ≥ 4 bone metastases including one beyond the axial skeleton vs. low: <4 bone metastases)
 Based on CHAARTED (ECOG 3805) criteria²⁴

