13.8 Analysis of Secondary Endpoints

Safety and Tolerability: All adverse events recorded during the trial will be summarized for the safety population. The incidence of events that is new or worsening from the time of first dose of treatment will be summarized according to system organ class term, severity (based on CTCAE version 4.0 grade), type of adverse event, and relation to study treatment. For the combination therapy, special interests include toxicities related to induction of immune phenomenon such as pneumonitis, colitis, and severe rash. The frequency of AEs will be summarized separately according to treatment arms, with 90% exact binomial confidence intervals (CI). The proportion of patients in each arm with grade 4 or higher AEs will also be reported with an exact binomial 90% CI.

Deaths reportable as SAEs and non-fatal serious adverse events will be listed by patient and tabulated by primary system organ class, and type of adverse event.

PFS and OS: The distributions of time to PSA progression, PFS and OS will each be summarized using the product-limit method of Kaplan-Meier according to treatment arms. Median times for each endpoint will be presented with two-sided 95% confidence intervals estimated using log(-log(survival)) methodology. Kaplan-Meier estimates of the endpoints at 6 or 12 months after treatment initiation may also be presented with two-sided 95% confidence intervals.

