13.9 Analysis of Exploratory Clinical Endpoints

The endpoints will be summarized descriptively and graphically by treatment assignment. Tests for intra-patient changes in values while on combination treatment will use Wilcoxon signed-rank for continuous endpoints; categorical endpoints at two timepoints will be cross-tabulated and relevant proportions will be reported with confidence intervals. Changes in values will also be compared between treatment groups using the Wilcoxon rank sum tests for continuous endpoints. The Kaplan-Meier method will be employed to characterize the distributions of time to event endpoints.

Specifically,

Time to PSA progression: the distributions of time to PSA progression will be summarized using Kaplan-Meier according to treatment arms. Median times to PSA progression will be presented with two-sided 95% confidence intervals.

PSA response: the proportion of patients with a PSA response will be presented with a two-sided 95% confidence interval **(CI)** using exact binominal method according to the treatment arms. Change in PSA will also be summarized descriptively according to the treatment arms and the changes in PSA will also be compared between treatment groups using the Wilcoxon rank sum tests.

Symptomatic skeletal events (SSEs): the proportion of patients with SSEs will be presented with a two-sided 95% confidence interval (CI) using exact binominal method and the distributions of time to first SSEs will be summarized using Kaplan-Meier plots according to the treatment arms.

Quality of life: descriptive statistics at each time point and changes over time will be provided for quality of life, pain and analgesic use measures. Mixed models may be used to explore the impact of time on quality of life and pain adjusting for treatment arms and other relevant factors.

Time to introduction of analgesic use will be summarized using Kaplan-Meier plots according to the treatment arms.

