13.12.2 Evaluation of the Primary Efficacy Endpoint

There is no primary efficacy endpoint.

Analyses of secondary efficacy endpoints will be on an intent-to-treat basis. Specifically, all eligible participants included in the study must be assessed for response/outcome to therapy, even if there are major protocol therapy deviations.

Subanalyses may then be performed on the basis of a subset of participants,

excluding those for whom major protocol deviations have been identified (e.g., early death due to other reasons, early discontinuation of treatment, major protocol violations, etc.). However, these subanalyses may not serve as the basis for drawing conclusions concerning treatment efficacy, and the reasons for excluding participants from the analysis should be clearly reported. If applicable to the endpoint, the 95% confidence intervals will be provided.

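### Section 13.8 summarizes PFS and OS arm by arm only, so this randomized trial plans no treatment-effect estimate for either endpoint, and the two randomization factors are not used in any analysis.

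*Combined protocol and SAP*

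**What the plan says.** Section 13.1 describes the design: "This is an open label phase 2 trial that randomizes 45 mCRPC patients (2:1 ratio", with radium-223 alone as the control. Section 13.3 adds "Patients will be stratified based on" and lists alkaline phosphatase (cut at 220) and volume of bone metastases.

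The secondary efficacy objective in Section 1.3 is "To preliminarily investigate the efficacy of the combination of pembrolizumab plus radium-223 as evaluated by progression-free survival (PFS) and overall survival (OS".

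For the analysis, Section 13.8 says that time to PSA progression, PFS and OS "will each be summarized using the product-limit method of Kaplan-Meier according to treatment arms". It continues: "Median times for each endpoint will be presented with two-sided 95% confidence intervals estimated using log(-log(survival)) methodology". Estimates at 6 or 12 months are optional. Nothing else is planned for PFS or OS by arm.

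Section 13.12.2 puts the secondary efficacy endpoints on an intent-to-treat basis.

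**The concern.** A randomized control arm makes an unconfounded contrast possible. Section 13.8 describes each arm and stops short of that contrast. Two medians with separate intervals do not give an effect estimate or its uncertainty, so a reader who wants to know what adding pembrolizumab did to PFS or OS must work it out informally, with one of the two medians coming from about 15 patients.

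The plan also stratifies randomization on two factors and then names neither in any analysis. And because the trial is open label, a contrast that is not fixed in advance can be chosen after the data have been seen.

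**Working it through.** **1. Which contrasts does Section 13 plan?**

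- 13.7, T-cell infiltration, Arm A vs Arm B: rank-sum test, difference with 95% CI; randomization factors not used.
- 13.8, PFS and OS by arm: Kaplan-Meier curves, medians, optional 6- or 12-month estimates; no contrast.
- 13.9, exploratory endpoints: rank-sum test between arms for continuous measures; Kaplan-Meier only for times to event. An optional quality-of-life mixed model adjusts for arm and for further factors that are not named.
- 13.11, PFS by DNA-repair mutation status: log-rank test.
- 13.11, PFS by change in cf-DNA tumor purity, in patients event-free at week 13: Cox hazard ratio with 95% CI.

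So the only PFS contrasts planned are between groups not formed by randomization. Alkaline phosphatase and bone volume appear as randomization factors in the schema, 5.1 and 13.3, and in no analysis.

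**2. Is there a stated figure to reproduce?** Not for this comparison: the plan gives no effect size, event count or power for PFS or OS by arm. The nearest is Table 21, first row (mutation groups: 36 events, HR 0.50, prevalence 0.3, one-sided 0.15). Power = Φ(√(36 × 0.3 × 0.7) × ln 2 − 1.036) = Φ(1.906 − 1.036) = 0.81, against 0.80 stated. It reproduces, but says nothing about Arm A vs Arm B.

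**3. What event counts are plausible?** This is an assumption. Take 45 patients, uniform accrual over A = 18 months, F = 6 further months (upper end of the accrual time in 13.2), exponential times, one median for both arms and no loss. Then

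events = 45 × {1 − [exp(−λF) − exp(−λ(F + A))] / (λA)}, with λ = ln 2 / median.

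- Median 6 months (the non-mutated PFS median in Table 21): 45 × (1 − 0.4375/2.079) = 35.5.
- Median 14.9 months (phase 3 radium-223 survival, Section 2.2.1): 45 × (1 − 0.429/0.837) = 21.9.
- With F = 24 months, the same medians give 43.8 and 35.0.

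A range of 20 to 45 events covers these.

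**4. How precise would the hazard ratio be?** If events split in the 2:1 allocation ratio, SE(log HR) = 1/√(events × 2/3 × 1/3), and the 95% CI is the estimate times or divided by exp(1.96 × SE).

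- 20 events: SE 0.474, factor 2.53
- 30 events: SE 0.387, factor 2.14
- 36 events: SE 0.354, factor 2.00
- 45 events: SE 0.316, factor 1.86

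At 36 events an observed HR of 0.70 would carry an interval of 0.35 to 1.40.

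**5. Could it serve as a test?** Power at two-sided 0.05 is Φ(|ln HR|/SE − 1.96). For HR 0.50 it is 31% at 20 events, 50% at 36 and 59% at 45; for HR 0.70 it is 11% to 20% over that range. Power of 80% needs (1.96 + 0.842)² / [(2/9)(ln HR)²] events: 74 for HR 0.50 and 278 for HR 0.70, in a trial of 45 patients. The contrast is usable as an estimate and not as a confirmatory test.

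**6. Stratify the model or adjust?** Two binary factors make four cells. With 15 controls that averages 15/4 = 3.75 per cell, too sparse for a stratified Cox model. Entering them as covariates gives three terms including arm, or 20/3 ≈ 7 to 45/3 = 15 events per term.

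**The case against.** The best defence is that the plan does what its objective says. The primary objective in 1.2 is to compare; the secondary one is only to investigate efficacy in a preliminary way. Section 13.12.2 states that there is no primary efficacy endpoint, and 13.4 sizes the trial on T-cell infiltration alone. On that view, description by arm is a deliberate choice for a small biomarker trial. This stands as far as it goes: it rules out calling the omission a contradiction, and it limits the remedy to estimation. It does not explain why a PFS hazard ratio is worth reporting for change in tumor purity but not for the randomized treatment.

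Several stronger readings are tempting, and the documents do not support them.

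- A reader might infer that exploratory endpoints are treated better than PFS and OS. For times to event they are not: "The Kaplan-Meier method will be employed to characterize the distributions of time to event endpoints".
- A reader might take "these subanalyses may not serve as the basis for drawing conclusions concerning treatment efficacy" to mean that the intent-to-treat analysis is meant to support an efficacy conclusion. That sentence only restricts subset analyses that exclude major deviations; it promises no between-arm conclusion.
- A reader might suppose that the arms will be judged by whether the two median intervals overlap. The plan contains no such rule, so its error rates cannot be charged to the plan.
- A reader might argue that analysis must use the factors because they are strongly prognostic. Section 2.2.1 shows that the phase 3 analysis stratified and adjusted for total alkaline phosphatase, but the documents do not quantify the prognostic effect of either factor.

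Practical objections also have force. Patients with four or more lesions, all axial, fit neither volume category as worded. Section 5.5 does not require follow-up scans for patients who have not progressed, and treatment can last much longer in Arm A (up to 35 pembrolizumab doses) than in Arm B (up to 6 radium-223 doses), so a PFS contrast could partly reflect unequal assessment. That limits how a hazard ratio is read, but it affects the two medians equally and is no reason to prefer them.

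**Conclusion.** The point holds as a moderate weakness of omission. No stated figure is wrong and no passage is contradicted, but the secondary efficacy endpoints have no planned treatment-effect estimate, and the randomization factors, although used to allocate patients, are not used in any analysis.

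The gain from repair is limited. It yields an effect with an honest interval, roughly a factor of two either way, and not evidence that could settle efficacy. That width rests on assumed event totals and on events splitting 2:1, which fits a hazard ratio near 1; a real effect would change both somewhat. The omission itself does not depend on these assumptions.

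**What to change.** Keep the Kaplan-Meier summaries and add to Section 13.8:

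- For PFS and for OS, the Arm A vs Arm B hazard ratio with 95% CI, on the intent-to-treat basis of 13.12.2.
- A Cox model with alkaline phosphatase and bone-metastasis volume as covariates, as recorded at randomization, rather than stratified on four sparse cells.
- The unadjusted hazard ratio alongside.
- A statement that these are preliminary estimates with no confirmatory test.

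Reconcile two conflicts in the same edit, since the hazard ratio cannot be computed unambiguously without this:

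- **Population.** Section 13.6 restricts secondary endpoints to treated patients with biopsies at both times, which 13.4 puts at about 36 (24 and 12). Section 13.12.2 says intent-to-treat, which starts from 45 (30 and 15).
- **PFS start.** Section 13.1 counts from first dose; 11.1.8 counts from randomization (or registration), and the genomic endpoint definition in 13.1 from randomization. Section 5.1 asks for treatment within 7 days of randomization, so the gap should be short, but a patient who is randomized and never treated has no first-dose date.

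The cost is a few lines of text and modest programming, with no new patients or data. The downside is a wide interval that must be presented as such.

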13.9 Analysis of Exploratory Clinical Endpoints

The endpoints will be summarized descriptively and graphically by treatment assignment. Tests for intra-patient changes in values while on combination treatment will use Wilcoxon signed-rank for continuous endpoints; categorical endpoints at two timepoints will be cross-tabulated and relevant proportions will be reported with confidence intervals. Changes in values will also be compared between treatment groups using the Wilcoxon rank sum tests for continuous endpoints. The Kaplan-Meier method will be employed to characterize the distributions of time to event endpoints.

Specifically,

Time to PSA progression: the distributions of time to PSA progression will be summarized using Kaplan-Meier according to treatment arms. Median times to PSA progression will be presented with two-sided 95% confidence intervals.

PSA response: the proportion of patients with a PSA response will be presented with a two-sided 95% confidence interval **(CI)** using exact binominal method according to the treatment arms. Change in PSA will also be summarized descriptively according to the treatment arms and the changes in PSA will also be compared between treatment groups using the Wilcoxon rank sum tests.

Symptomatic skeletal events (SSEs): the proportion of patients with SSEs will be presented with a two-sided 95% confidence interval (CI) using exact binominal method and the distributions of time to first SSEs will be summarized using Kaplan-Meier plots according to the treatment arms.

Quality of life: descriptive statistics at each time point and changes over time will be provided for quality of life, pain and analgesic use measures. Mixed models may be used to explore the impact of time on quality of life and pain adjusting for treatment arms and other relevant factors.

Time to introduction of analgesic use will be summarized using Kaplan-Meier plots according to the treatment arms.

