2.2 Study Agents

2.2.1 **Radium-223 (Xofigo)³**

Radium-223 is a calcium mimetic that hones in on bone metastases due to their high rate of bone turnover. It binds to new bone stroma and emits alpha particles, which induce double-stranded DNA breaks that result in tumor cell death.² The short path length of alpha particles limits toxicity to surrounding healthy tissue. Overall, radium-223 is well tolerated. The most frequently observed adverse events (AEs) of any grade in the phase 3 study were anemia (31%), thrombocytopenia (12%), constipation (18%), diarrhea (25%), nausea (36%), vomiting (18%), fatigue (26%), peripheral edema (13%), anorexia (17%), and bone pain (50%). Compared to placebo, radium-223 increased median overall survival from 11.3 months to 14.9 months and reduced the risk of death by 30% (HR: 0.70; 95%CI: 0.58-0.83; p<0.001).² Radium-223 has also been shown to significantly increase the median time to the first symptomatic skeletal event (15.6 vs. 9.8 months) and the time to increase in total alkaline phosphatase (7.4 vs. 3.8 mo.) Compared to placebo, it elicited a higher rate of normalization of serum alkaline phosphatase (34 vs. 1%) and PSA declines \geq 30% (16% vs. 6%).

Description

Radium Ra 223 dichloride is an alpha particle-emitting radiopharmaceutical.

Radium-223 is supplied as a clear, colorless, isotonic, and sterile solution to be administered intravenously with pH between 6 and 8. Each milliliter of solution contains 1,000 kBq radium-223 dichloride (27 microcurie), corresponding to 0.53 ng radium-223, at the reference date. Radium is present in the solution as a free divalent cation.

Each vial contains 6 mL of solution (6,000 kBq (162 microcurie) radium-223 dichloride at the reference date). The inactive ingredients are 6.3 mg/mL sodium chloride USP (tonicity agent), 7.2 mg/mL sodium citrate USP (for pH adjustment),

0.2 mg/mL hydrochloric acid USP (for pH adjustment), and water for injection USP.

The molecular weight of radium-223 dichloride, ²²³RaCl₂, is 293.9 g/mol.

Radium-223 has a half-life of 11.4 days. The specific activity of radium-223 is 1.9 MBq (51.4 microcurie)/ng.

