9.2 Symptomatic Skeletal Events (SSEs)

SSEs will be defined as the use of external beam radiation to relieve bone pain, occurrence of new/symptomatic pathologic fracture, occurrence of spinal cord compression, or tumor-related orthopedic surgical intervention (secondary to a complication of a bone metastasis).

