L: Diagnostic CT chest and CT or MRI of the abdomen and pelvis and bone scan including SPECT/CT should be obtained at baseline and every 12 weeks (+/- 7 days). (NOTE: SPECT/CT will be done only at DFCI.) Scans should remain on an every 12 week schedule (+/- 7 days) even if dose delays occur.

M*: Correlative immune studies: will be obtained and transported overnight at room temperature to the [name] Lab at UCSF. Samples for immune studies will be done at week 1 (pre-dose), week 5, week 9, week 13, week 21 and at the time of progression for those patients still on study.

N: Bone biopsy: archival tissue is permitted for baseline analysis. IR guided bone biopsy will be done at week 8 (+3 weeks) after the second dose of radium-223. If the second dose cannot be given for safety reasons, biopsy should still be performed within the window detailed here.

O: Blood samples for cell free DNA (cf-DNA) will be performed at treatment initiation (week 1, pre-dose), on treatment (week 5 and 13), and at time of progression.

P: Quality of life, pain and analgesic use will be measured via the FACT-P (Appendix B), Brief Pain Inventory (Short Form) (Appendix C), and analgesic diary (Appendix D) prior to treatment, at week 5, 9, then every 6-8 weeks after week 9 (as schedules differ between the two arms), and at treatment progression/off study visit.

Q: After progression/treatment discontinuation, follow the participant for survival, receipt of next line therapies, and post-treatment SSEs every 6 months until death or 2 years after treatment discontinuation.

R: Arm A study assessments will continue based on the same schedule as detailed for weeks 1-13 when pembrolizumab is given alone (e.g., visits, labs, assessments every 3 weeks only). If radium-223 is resumed upon progression, assessment schedule and radium-223 + pembrolizumab dosing will resume based on the schedule detailed for weeks 1-13. Arm B study assessments and radium-223 dosing will continue based on the same schedule detailed for weeks 1-13 up to 6 doses without breaks except for toxicity/intolerance (Section 6.2).

Note: For both arms: Immune studies will follow the schedule detailed in footnote M*

S: End of Treatment visit should occur within 30 days after last study treatment.

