11.1.8 Evaluation of Time to Event Endpoints

Progression-Free Survival: Progression-Free Survival (PFS) is defined as the time from randomization (or registration) to the earlier of progression or death due to

any cause. Participants alive without disease progression are censored at date of last disease evaluation.

Time to Progression: Time to Progression (TTP) is defined as the time from randomization (or registration) to progression, or censored at date of last disease evaluation for those without progression reported.

Overall Survival: Overall Survival (OS) is defined as the time from randomization (or registration) to death due to any cause, or censored at date last known alive.

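### Time to first symptomatic skeletal event is summarised by Kaplan-Meier with no allowance for death as a competing event (low severity)

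*Combined protocol and SAP*

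**What the plan says.** SSEs are an exploratory clinical endpoint. Section 13.1 lists it as "Rate of SSEs and time to first SSE", in line with the objective in Section 1.4. The definition in Section 9.2 begins "SSEs will be defined as the use of external beam radiation to relieve bone pain" and goes on to pathologic fracture, cord compression and orthopedic surgery. Death is not a component.

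Section 13.9 plans two summaries. One is a binomial proportion: "the proportion of patients with SSEs will be presented with a two-sided 95% confidence interval (CI) using exact binominal method". The other is graphical: "the distributions of time to first SSEs will be summarized using Kaplan-Meier plots according to the treatment arms". No between-arm test of SSEs is planned.

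Section 11.1.8 gives origins and censoring rules for PFS, time to progression and OS only. Time to progression, for example, is "censored at date of last disease evaluation for those without progression reported". Time to first SSE has no stated origin, censoring rule or handling of death. The origin cannot be borrowed safely from PFS, which runs from randomization in Section 11.1.8 and from first dose in Section 13.1. No competing-risk method appears anywhere.

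On follow-up, footnote Q of the Study Calendar (Section 10) asks that men be followed after treatment for survival, "receipt of next line therapies, and post-treatment SSEs every 6 months until death or 2 years after treatment discontinuation". Section 13.2 instead plans 6 months of follow-up after accrual and a study of 2 years in total.

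**The concern.** A man who dies without an SSE can no longer have one. Kaplan-Meier with deaths censored treats him as if he still could, so 1-KM estimates SSE risk in a setting where nobody dies. Where death is common, that exceeds the share of men who actually have an SSE. Section 2.2.1 puts the two medians on radium-223 less than a month apart, so the gap could be material.

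The crude proportion raises a separate question: what period does it cover? Under footnote Q the window ends 2 years after treatment stops, not at a fixed time from randomization. Treatment can last 24 months in Arm A (Section 5.4) but at most six four-weekly doses in Arm B. Contact differs too: every 3 weeks on pembrolizumab alone, against every 6 months once treatment has ended.

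At stake is how the Section 1.4 objective on SSE rate and timing is answered. The two planned summaries could give quite different impressions, with nothing in the plan to say which one estimates the risk of an SSE.

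**Working it through.** The plan states no SSE rate, event count or power, so there is no figure to reproduce. What follows is an illustration.

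**Inputs.** Section 2.2.1: median time to first SSE 15.6 months and median OS 14.9 months, both on radium-223. Assumptions: these medians carry over to this trial; hazards are constant; the SSE median comes from an estimate with deaths censored; the hazard of death before an SSE is a fraction f of the overall death hazard. OS includes deaths after an SSE, which do not compete, so f = 1 is an upper-end value; f is varied from 0.25 to 1.

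**Formulas.**
- SSE hazard a = ln2/15.6 = 0.0444 per month
- Death hazard b = f × ln2/14.9 = f × 0.0465 per month
- 1-KM(t) = 1 − exp(−a·t)
- Cumulative incidence F(t) = a/(a+b) × [1 − exp(−(a+b)·t)]

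**Kaplan-Meier against cumulative incidence.** 1-KM is 41.3% at 12 months and 65.6% at 24 months. At f = 1, a+b = 0.0909 and a/(a+b) = 0.4885, so F(12) = 0.4885 × (1 − 0.336) = 32.5% and F(24) = 0.4885 × (1 − 0.113) = 43.3%.

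| f | F(12) | Excess at 12 mo | F(24) | Excess at 24 mo |
|---|---|---|---|---|
| 0.25 | 38.8% | 2.5 points | 58.6% | 7.0 points |
| 0.50 | 36.5% | 4.8 | 52.7% | 12.9 |
| 0.75 | 34.4% | 6.9 | 47.7% | 17.9 |
| 1.00 | 32.5% | 8.9 | 43.3% | 22.2 |

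(Differences are taken before rounding.)

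**Crude proportion.** Men who die without an SSE stay in the denominator as SSE-free, exactly as in F(t). With complete follow-up to time t, the expected proportion is therefore F(t). With staggered censoring it is lower. Assume follow-up uniform on 6 to 24 months (18 months of accrual plus 6, from the upper end of Section 13.2). The expected proportion at f = 1 is then the average of F over that range: 0.4885 × [1 − (0.579 − 0.113)/(0.0909 × 18)] = 34.9%, against F(24) = 43.3%.

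**Unequal windows, identical hazards in both arms (f = 1).** Arm B: 20 weeks from first to sixth dose is 4.6 months, plus 24 gives 28.6 months and F = 45.2%. Arm A with 6, 12 or 24 months of treatment, plus 24: F = 45.7%, 47.0% or 48.2%. The largest spurious gap is 48.2 − 45.2 = 3.0 points. It is small because only exp(−0.0909 × 28.6) = 7% of men are still alive and SSE-free at 28.6 months.

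**Precision.** Exact 95% intervals: 5/15 gives 11.8% to 61.6%; 10/30 gives 17.3% to 52.8%.

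**The case against.** The strongest reply is that the plan never promises a 1-KM incidence. For SSEs, Section 13.9 offers plots only; the optional 6- and 12-month Kaplan-Meier estimates in Section 13.8 concern PSA progression, PFS and OS. Kaplan-Meier with deaths censored remains a valid description of the cause-specific hazard, and the error arises only when the curve is read as the share affected. That stands. It makes the problem one of interpretation, although a rate objective answered by such a plot invites that reading.

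It can also be said that the medians come from another trial, in men with symptomatic bone metastases, whereas Section 3.2 requires only metastatic disease on bone scan, and that Section 13.2's timeline barely reaches 24 months. Both points are fair. They are why the size is given as a range and why the 12-month figures matter more. Sampling error also exceeds these biases at this sample size, but a wide interval does not correct an estimate aimed at a different quantity.

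Two stronger readings are tempting, and the documents do not support them:
- A reader might infer that both summaries overstate SSE incidence. The crude proportion does not: counting men who die without an SSE as SSE-free is correct, and censoring can only lower it.
- A reader might infer that the crude proportions cannot be compared because follow-up runs to about 29 months in Arm B and 48 in Arm A. Those are maxima derived from the treatment limits, not stated or expected windows. If footnote Q is followed, the resulting gap is at most about 3 points, and a common data cut-off under Section 13.2 would make follow-up similar by arm.

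**Conclusion.** The point holds for Kaplan-Meier. Section 13.9 makes no allowance for death, and 1-KM read as incidence would be too high by about 2.5 to 9 points at 12 months and 7 to 22 points at 24 months. That range rests on constant hazards, on the background medians applying here, and on death before an SSE running at 25% to 100% of overall mortality.

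The crude proportion has a different and lesser fault. It is correct under complete follow-up and too low under censoring, but it has no time horizon, and its window depends on when treatment stops. The likely distortion between arms is at most about 3 points if footnote Q is followed.

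Severity is low. The endpoint is exploratory and descriptive, the arms have about 30 and 15 patients, and no between-arm SSE test or other planned inference depends on it. The change is worth making because the better estimate uses data already being collected.

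**What to change.** In Section 13.9:
1. Define time to first SSE from randomization, with an explicit censoring rule and death without an SSE as a competing event.
2. Report the Aalen-Johansen cumulative incidence by arm with 95% CIs at fixed times that follow-up supports, such as 6 and 12 months. If Kaplan-Meier plots are kept, state that they are not to be read as the share of men affected.
3. Either tie the crude proportion to a fixed window from randomization, or present it with follow-up time and the number of deaths without an SSE in each arm.

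Separately, reconcile footnote Q of the Study Calendar with Section 13.2, so that the period over which SSEs are counted is clear.

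The cost is SAP wording. Footnote Q already provides for collecting survival and post-treatment SSEs, so no new data are needed.
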